8.2 Hypothesis Testing and Determination of Sample Size

The following hypothesis will be tested:

$$H_0: p \leq 0.6$$

Against the alternative

$$H_A: p > 0.6$$

Where p is the proportion of subjects with successful haemostatic efficacy (i.e.; 'excellent' or 'good').

The null hypothesis will be tested against the alternative by comparing the lower limit of the two-sided 95% Blyth-Still-Casella confidence interval for the proportion of patients with successful haemostatic efficacy with the predefined threshold of 0.6.

Due to practical limitations in subject enrolment and total study duration due to the very small number of patients with this indication, no real sample size calculation was performed on basis of statistical power considerations. Instead, the probabilities and associated confidence intervals (CIs) for different outcomes are provided, assuming a true success rate of 0.95.

Assuming that the study treatment is successful (i.e. the haemostatic efficacy assessment is 'excellent' or 'good') in 95% of the subjects, the success rates given in Table 1 will be observed in the 24 study subjects with the following probabilities:

Table 1: Overall clinical assessment of haemostatic efficacy

Outcome (n/N)	Percentage	Probability for the outcome (binomial)	95% (2-sided) confidence interval ^a
≥19/24	≥79.1%	0.999	0.594–0.914
≥20/24	≥83.3%	0.994	0.633–0.941
≥21/24	≥87.5%	0.970	0.691–0.965
≥22/24	≥91.7%	0.884	0.744–0.985

n = number of subjects with 'excellent' and 'good' haemostatic efficacy; N = total number of subjects.

^a Blyth-Still-Casella interval, realised by StatXact® software.

Hence, assuming that treatment with Octafibrin is associated with a true success rate of 95% of the 24 subjects, there will be a 99.4% probability that at least 20 of 24 subjects will have a successful assessment. In case of 20 successful assessments, the lower boundary of the 95% CI will be 0.633, i.e., > 60%.

FORMA-02	JSS Medical Research - Data Management	 <small>RESPONSIVE RELIABLE RESULTS</small>	
Statistical Analysis Plan			
Form Number: MNI-DM-BIS-01 v 6.0-T1	Current Version Number: 2.0	Previous Version Number: 1.1 9-April-2015	Date: 11-July-2016

For the purpose of analysis, the efficacy assessment made by the investigator on the 4-point rating scale will be transformed to a dichotomous endpoint, with 'treatment success—yes' defined as a rating of 'excellent' or 'good' and 'treatment success—no' defined as a rating of 'moderate,' 'none,' or a missing rating. The success rate will be calculated as the proportion of patients with treatment success.

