3.2 Study Endpoints

3.2.1 Primary Endpoint

The primary endpoint is:

- The primary endpoint is the overall clinical assessment of haemostatic efficacy of Octafibrin in treating the first documented bleeding episode of each patient. The first bleeding episode covers the time period from the first Octafibrin infusion until 24 hours (i.e., 1 day) after the last infusion or the end of the treatment observation period, whichever comes last.

The investigator's overall clinical assessment of haemostatic efficacy for bleeding will be based on a 4-point haemostatic efficacy scale (see table below). The final efficacy assessment of each patient will be adjudicated by the Independent Data Monitoring & Endpoint Adjudication Committee (IDMEAC). The number of subjects per outcome category will be assessed in the final analysis.

Category	Definition
Excellent	Immediate and complete cessation of bleeding in the absence of other haemostatic intervention as clinically assessed by the treating physician; and/or <10% drop in haemoglobin compared to pre-infusion.
Good	Eventual complete cessation of bleeding in the absence of other haemostatic intervention as clinically assessed by the treating physician; and/or <20% drop in haemoglobin compared to pre-infusion.
Moderate	Incomplete cessation of bleeding and additional haemostatic intervention required, as clinically assessed by the treating physician; and/or between 20 and 25% drop in haemoglobin compared to pre- infusion.
None	No cessation of bleeding and alternative haemostatic intervention required, as clinically assessed by the treating physician; and/or >25% drop in haemoglobin compared to pre-infusion.

FORMA-02	JSS Medical Research - Data Management		
Statistical Analysis Plan			
Form Number: MNI-DM-BIS-01 v 6.0-T1	Current Version Number: 2.0	Previous Version Number: 1.1 9-April-2015	Date:11-July-2016

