3.2.2 Secondary Endpoints

The secondary efficacy endpoints are:

- MCF assessment before first infusion and 1 hour after end of first and last infusion of each documented bleeding episode.
- Fibrinogen plasma level before and 1 hour after the end of each infusion as well as at the time of the overall clinical assessment of haemostatic efficacy (i.e., 24 hours after the last infusion of each documented bleeding episode).
- Response as indicated by incremental IVR, calculated as the maximum increase in plasma fibrinogen (Clauss data) between pre-infusion and 1 and 3 hours post-infusion.
- Efficacy of Octafibrin in all bleeding episodes collected in the study using the investigator's overall clinical assessment of haemostatic efficacy for bleeding based on a 4-point haemostatic efficacy scale.

Efficacy of Octafibrin in surgical prophylaxis will be assessed at the end of surgery by the surgeon and post-operatively by the hematologist using the following scales:

Category	Definition
Intra-operative efficacy as assessed by surgeon (at the end of the surgery = after last suture)	
Excellent	Intra-operative blood loss* was lower than or equal to the average expected blood loss for the type of procedure performed in a subject with normal haemostasis and of the same sex, age, and stature.
Good	Intra-operative blood loss* was higher than average expected blood loss but lower or equal to the maximal expected blood loss for the type of procedure in a subject with normal haemostasis.
Moderate	Intra-operative blood loss* was higher than maximal expected blood loss for the type of procedure performed in a subject with normal haemostasis, but haemostasis was controlled.
None	Haemostasis was uncontrolled necessitating a change in clotting factor replacement regimen.

*All excludes unexpected blood loss due to surgical complications, i.e.,

- Direct injury of a vessel (artery or vein)
- Vessel injury not adequately responding to routine surgical procedures achieving haemostasis
- Accidental injury of parenchymatous tissue (e.g., liver, lung)

FORMA-02	JSS Medical Research - Data Management	 RESPONSIVE RELIABLE RESULTS
Statistical Analysis Plan		
Form Number: MNI-DM-BIS-01 v 6.0-T1	Current Version Number: 2.0	Previous Version Number: 1.1 9-April-2015
Date:11-July-2016		

Post-operative efficacy as assessed by haematologist

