Excellent	No post-operative bleeding or oozing that was not due to complications of surgery. All post-operative bleeding (due to complications of surgery) was controlled with Octafibrin as anticipated for the type of procedure.
Good	No post-operative bleeding or oozing that was not due to complications of surgery. Control of post-operative bleeding due to complications of surgery required increased dosing with Octafibrin or additional infusions, not originally anticipated for the type of procedure.
Moderate	Some post-operative bleeding and oozing that was not due to complications of surgery; control of post-operative bleeding required increased dosing with Octafibrin or additional infusions, not originally anticipated for the type of procedure.
None	Extensive uncontrolled post-operative bleeding and oozing. Control of post-operative bleeding required use of an alternate fibrinogen concentrate.

An overall efficacy assessment taking both the intra- and post-operative assessment into account will be adjudicated by the IDMEAC. In the event that any intra- or post-operative endpoint data differ between the investigator's assessment and the adjudicated assessment by the IDMEAC, the endpoint will be that based on the adjudicated assessments based on an agreed algorithm as indicated in the IDMEAC charter.

The surgical observation period starts with the first dose of Octafibrin administered prior to elective surgery (Day 1) and, depending on the severity of the event, will last at least 3 post-operative days for minor and 7 post-operative days for major surgeries or until the day of the last post-operative infusion, whichever comes last.

In addition, the location, severity and type of surgery will be documented. Expected and actual duration of surgical procedure and details of administered dose(s) of Octafibrin (pre-, intra- and/or post-operatively) will be recorded. Fibrinogen plasma levels (pre-, intra-, and post-operatively) will be measured. Details of concomitantly administered products (except standard anaesthesia) along with a brief narrative describing the outcome of the intervention will be recorded.

The safety endpoints are:

- Vital signs.
- Physical examination.
- Check of Wells criteria for deep venous thrombosis (DVT) and PE (pulmonary embolism).
- Routine clinical laboratory assessment, including coagulation parameters.
- Adverse events (AEs), including thromboembolic complications and early signs of allergic or hypersensitivity reactions.

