6.2 Derived and Computed Variables

It is expected that variables will be derived and computed. The SAP will not be amended for additional variables that are not related to the primary or key secondary variables.

For analysis purpose the assessment made by the investigator on the 4-point rating scale will be transformed to a dichotomous endpoint with success as "Yes" defined as a rating of excellent or good and "No" as Moderate or Non or Missing). The success rate will be calculated as the proportion of patients with success.

Any additional derived variables will be identified and documented in the Statistical Analysis System (SAS®) programs that create analysis files.

The following variable will be calculated for the analysis tables: BMI

Variable Name	Description	Valid Values (Ranges)	Computation Methods, Notes, or Equation(s)
BMI	Body Mass Index	—	$BMI = \{\text{Weight (in Kg)} / (\text{Height (in meters)})^2\}$
Success	Overall clinical assessment of haemostatic efficacy	Yes/No	if value is 'excellent; or 'good', then Success = "Yes" if value is 'Moderate 'or 'None' or 'Missing', then Success = "No"

Body Mass Index (BMI) = $\{\text{Weight (in Kg)} / (\text{Height (in meters)})^2\}$

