8 EFFICACY ANALYSIS

8.1 Primary Efficacy Analysis

For bleeding efficacy, the primary endpoint is the overall clinical assessment of the haemostatic efficacy of Octafibrin in treating the first documented bleeding episode of each patient.

The first bleeding episode covers the time period from the first Octafibrin infusion until 24 hours (i.e., 1 day) after the last infusion or the end of the treatment observation period, whichever comes last. Frequency distribution will be provided for the haemostatic efficacy scale data. In addition, a 95% CI for the success rate in haemostatic efficacy (excellent or good) according to Casella (Blyth-Still-Casella interval) will be computed using StatXact® software.

For the following subjects the haemostatic efficacy outcome will be set to the worst category i.e., "none":

- Subjects who withdraw from the study due to lack of efficacy.
- Subjects receiving cryoprecipitate, or concentrates containing fibrinogen other than the IMP between first infusion and efficacy assessment (unless it is clearly documented that these products were administered for reasons unrelated to efficacy [e.g., pharmacy error]).
- Subjects with missing haemostatic efficacy assessment.

Haemostatic efficacy will be displayed by co variables (sex, age groups, race, weight and type of bleeding) in tables or with co variables in listings depending on the number per subgroup.

FORMA-02	JSS Medical Research - Data Management		
Statistical Analysis Plan			
Form Number: MNI-DM-BIS-01 v 6.0-T1	Current Version Number: 2.0	Previous Version Number: 1.1 9-April-2015	Date: 11-July-2016

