8.3.5 Surgical Prophylaxis

Efficacy of Octafibrin in surgical prophylaxis will be assessed intra-operatively (at the end of surgery = after last suture) by the surgeon and post-operatively by the haematologist using two 4-point efficacy scales. In the event that any intra- or post-operative endpoint data differ between the Investigator's assessment and the adjudicated assessment by the IDMEAC, the primary endpoint will be that based on the adjudicated assessments. The efficacy of Octafibrin in surgical prophylaxis will be evaluated by descriptive statistics based on an overall assessment.

In the documentation of the adjudication process for the assessment of surgical prophylaxis the DMEAC will explicitly identify any subjects for whom they considered there to be "unexpected blood loss due to surgical complications" and if that consideration altered the 4-point assessment of surgical prophylaxis. This information will be analyzed both including (as a sensitivity analysis) and excluding unexpected blood loss if it occurs.

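### The SAP derives the primary success variable from the investigator's rating although the IDMEAC is to adjudicate it, and does not say which rating prevails for bleeding

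*SAP*

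**What the plan says.** **Who decides the bleeding outcome.** SAP 3.2.1 has the investigator rate the first bleed on the 4-point scale and then states: "The final efficacy assessment of each patient will be adjudicated by the Independent Data Monitoring & Endpoint Adjudication Committee (IDMEAC"). Protocol 8.8 makes the same committee responsible for adjudicating the primary and secondary efficacy endpoints.

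**Which rating is analysed.**
- SAP 6.2: "For analysis purpose the assessment made by the investigator on the 4-point rating scale will be transformed to a dichotomous endpoint".
- SAP 8.2, directly after the hypothesis and Table 1: "For the purpose of analysis, the efficacy assessment made by the investigator on the 4-point rating scale will be transformed to a dichotomous endpoint".
- The Success row of the table in SAP 6.2 names no rater: "if value is 'excellent; or 'good', then Success" is set to yes.
- SAP 8.1 also names no rater: "a 95% CI for the success rate in haemostatic efficacy (excellent or good) according to Casella (Blyth-Still-Casella interval) will be computed".

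**What happens on disagreement.** A rule exists for surgery. In SAP 3.2.2, where the investigator and the IDMEAC differ on intra- or post-operative data, "the endpoint will be that based on the adjudicated assessments based on an agreed algorithm as indicated in the IDMEAC charter". SAP 8.3.5 repeats it: "the primary endpoint will be that based on the adjudicated assessments". That sentence uses the term primary endpoint but is confined to intra- and post-operative data. Neither the SAP nor protocol v6.0 has a matching sentence for bleeding.

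**All bleeds.** SAP 3.2.2 lists "Efficacy of Octafibrin in all bleeding episodes collected in the study using the investigator's overall clinical assessment of haemostatic efficacy", while SAP 8.3.4 says all bleeds are handled as the first bleed is.

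Protocol v6.0 has the same unresolved pairing in its Study Outline (statistical analysis, primary endpoint) and in 9.1.

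**The concern.** The success variable is the only one in the trial that is tested against a threshold. Both SAP passages that name a rater for it name the investigator, so a programmer working from 6.2 and 8.2 would never bring the adjudicated value into the test. In an open-label, uncontrolled study, the headline result would then rest on the treating physician's own judgement, although an independent reading of the same endpoint is already planned.

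Disagreement across the success boundary is foreseeable. Each category on the scale joins its clinical and haemoglobin criteria with and/or. A bleed with incomplete cessation and additional intervention but a haemoglobin drop under 10% therefore fits the wording of both moderate and excellent.

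If the rater is not fixed beforehand, there are two candidate primary results and the choice between them could be made after both are known. The same uncertainty passes to the all-bleeds endpoint and to the correlation of MCF with the primary efficacy variable in SAP 8.3.1.

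**Working it through.** **Inputs (SAP 8.2).** N = 24; null success rate 0.6; two-sided 95% Blyth-Still-Casella interval; assumed true rate 0.95. The lower limits are taken as printed in Table 1: 0.633 for 20/24 and 0.594 for 19/24. The pass rule is therefore X ≥ 20.

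**Reproducing the SAP's figures.** With X ~ Binomial(24, 0.95):

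| Outcome | SAP Table 1 | Recomputed |
|---|---|---|
| ≥19/24 | 0.999 | 0.9990 |
| ≥20/24 | 0.994 | 0.9940 |
| ≥21/24 | 0.970 | 0.9702 |
| ≥22/24 | 0.884 | 0.8841 |

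All four agree. At the null rate of 0.60, P(X ≥ 20) = 0.0134.

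**How often one net reclassification could decide the result.** This is possible only at 20/24 (one net downgrade turns a pass into a fail) or at 19/24 (one net upgrade turns a fail into a pass). P(X = k) = C(24, k) p^k (1 − p)^(24 − k).

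| | p = 0.95 (SAP) | p = 0.90 |
|---|---|---|
| P(X = 20) | 10626 × 0.95^20 × 0.05^4 = 0.0238 | 0.1292 |
| P(X = 19) | 42504 × 0.95^19 × 0.05^5 = 0.0050 | 0.0574 |
| Sum | 0.0288 | 0.1866 |

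The value 0.90 is protocol v6.0's planning rate, which the SAP replaced. It serves here only to show sensitivity to a lower true rate.

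**Illustrative type I error if the investigator's rating is tested.** Let the adjudicated rate be 0.60, f the share of adjudicated failures that the investigator rates as success, and g the share of adjudicated successes rated as failure. The investigator's rate is p = 0.60(1 − g) + 0.40f. The values of f and g are assumptions; the documents give none.

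| f | g | p | P(X ≥ 20) |
|---|---|---|---|
| 0 | 0 | 0.60 | 0.0134 |
| 0.10 | 0 | 0.64 | 0.0340 |
| 0.20 | 0.10 | 0.62 | 0.0217 |
| 0.05 | 0.05 | 0.59 | 0.0105 |
| 0.10 | 0.10 | 0.58 | 0.0081 |

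One-directional leniency raises the error. Symmetric misrating lowers it.

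**The reverse view.** Suppose investigators rate 95% as success and the IDMEAC downgrades a share d of those and upgrades none. The adjudicated rate is then 0.95(1 − d), and P(≥20/24 adjudicated successes) is 0.994 at d = 0, 0.978 at 2%, 0.922 at 5% and 0.738 at 10%. These values of d are also assumptions.

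**The case against.** The strongest reply is that the passages describe two steps: the investigator rates, then the committee fixes the final value. SAP 3.2.1 speaks of the final assessment, protocol 8.8 gives the committee the primary endpoint, and protocol 9.4.2.4 extends adjudication to every haemostatic efficacy result. On that reading only a few words are missing from 6.2 and 8.2. This is probably what was intended, but the derivation text does not say it, and 9.4.2.4 is a surgical section with no precedence rule for bleeding.

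A second reply is that the rule may be in protocol v7.0 or the IDMEAC charter, neither of which was available. That stands as a limit on this point: what is shown is that the SAP and protocol v6.0 lack the rule. But SAP section 1 says its analyses supersede the protocol's statistical sections, so a rule placed there would compete with SAP text naming the investigator. The SAP cites the charter only for the surgical algorithm.

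A third reply is that the effect is small, and this largely stands. The 0.029 is the chance of reaching the boundary; a reversal also needs a net reclassification in the right direction. Disagreement within excellent/good, or within moderate/none, changes nothing. The SAP 8.1 rules that set the outcome to none (another fibrinogen product, withdrawal for lack of efficacy, missing assessment) apply whichever rating is used. The type I error scenarios rest on assumed misrating rates and do not establish inflation.

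**Conclusion.** The concern holds and should be fixed. As written, SAP 6.2 and 8.2 test the investigator's rating, SAP 3.2.1 calls for an adjudicated final assessment, and neither the SAP nor protocol v6.0 says which prevails for bleeding. The text of the available documents supports this with high confidence; it does not exclude a rule in protocol v7.0 or the charter.

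The expected effect on the pass/fail conclusion is limited. It comes chiefly from good/moderate disagreement at 19/24 or 20/24, which together have probability 0.029 if the true rate is 0.95 and more if it is lower. The size and sign of any type I error effect are unknown, because no disagreement rate is documented. Even when the conclusion does not change, the reported success rate and its interval depend on the rater.

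**What to change.** 1. In SAP 6.2 (text and Success table), 8.1 and 8.2, state that success for the first bleed is derived from the IDMEAC-adjudicated rating, which prevails where it differs from the investigator's. This follows SAP 3.2.1 and the SAP's own surgical rule. If protocol v7.0 or the charter already says so, cite it.
2. State that the 8.1 rules setting the outcome to none apply to that rating.
3. Require adjudication of every first bleed before database lock, so that no patient has only an investigator's rating. Keep the existing rule that a missing assessment counts as failure.
4. As sensitivity analyses, report the investigator-rated success rate with its 95% interval and an investigator-by-IDMEAC cross-tabulation.
5. In 8.3.4, name the rater for all bleeds and reconcile it with SAP 3.2.2.

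**Cost.** A few sentences and one extra table; the adjudication itself is already planned. The drawbacks are that database lock must wait for adjudication to finish, and that the headline rate may differ from the investigators' rate in either direction.

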8.3 Secondary Efficacy Analyses

8.3.1 Clot strength (MCF)

- Fibrinogen levels 1 hour after infusions of the IMP, MCF at baseline and at 1 hour after first and last infusion as well as changes of MCF from baseline will be summarized using descriptive statistics and displayed graphically. The course of laboratory data will be presented graphically. Mean changes in MCF will be described with 2-sided 95% CIs.
- Statistical analyses will also be performed separately for the predefined subgroups as well as separated for the subjects' clinical outcome represented by each step of the 4-point haemostatic efficacy scale (excellent, good, moderate, none) and the dichotomized haemostatic efficacy scale (excellent/good, moderate/none). Scatter plots will show MCF by haemostatic efficacy outcome.

Correlation with MCF and MCF Change:

- In addition, a correlation analysis between MCF and the haemostatic efficacy assessment will be performed. To evaluate the correlation between MCF and the primary efficacy variable Spearman correlation coefficients will be estimated for the correlation of the 4-point haemostatic efficacy with MCF and with MCF change.

Note: If there is almost no variation in haemostatic efficacy outcomes (e.g., if almost all of the outcomes are "excellent") there will be only low discriminatory power to show an association between MCF and haemostatic efficacy.

Octafibrin use

- The dose of the IMP used per day and in total will be summarized using descriptive statistics for minor and major bleeding events. Frequency of infusions and duration of treatment will also be summarized. The frequency of unscheduled infusions will be summarized descriptively.

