3.1.2 Secondary Objectives

- To show an association between the overall clinical assessment of haemostatic efficacy and the surrogate endpoint 'clot strength' or 'clot firmness' (referred to as 'Maximum Clot Firmness' [MCF]) that was used as a surrogate endpoint for haemostatic efficacy and determined via Thromboelastography (TEG) in the pivotal Pharmacokinetic (PK) study FORMA-01. Therefore, MCF as surrogate efficacy parameter will be determined before first infusion and 1 hour after the end of first and last infusion.
- To achieve peak target plasma fibrinogen level of 100 mg/dL in minor bleeds and 150 mg/dL for major bleeds 1 hour post-infusion.
- To determine the response to Octafibrin based on incremental in vivo recovery (IVR).
- To demonstrate the efficacy of Octafibrin in preventing bleeding during and after surgery.
- To assess the safety of Octafibrin in subjects with congenital fibrinogen deficiency, including immunogenicity, thromboembolic complications, and early signs of allergic or hypersensitivity reactions.

FORMA-02	JSS Medical Research - Data Management	 JSS <small>RESPONSIVE RELIABLE RESULTS</small>	
Statistical Analysis Plan			
Form Number: MNI-DM-BIS-01 v 6.0-T1	Current Version Number: 2.0	Previous Version Number: 1.1 9-April-2015	Date:11-July-2016

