8.3.4 Efficacy of Octafibrin in All Bleeding Episodes

The efficacy of Octafibrin in the treatment of all bleeding episodes recorded throughout the study observation period will be assessed in the same way as the efficacy of Octafibrin in the treatment of the first bleeding episode per patient (see Section 9.4.1).

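### As worded, SAP 8.3.1 correlates MCF with efficacy on the first bleed only (about 24 pairs), and no clustered all-bleeds correlation is planned although the data are collected

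*SAP*

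**What the plan says.** SAP 3.1.2 lists as a secondary objective "To show an association between the overall clinical assessment of haemostatic efficacy and the surrogate endpoint" of clot firmness (MCF), which served as the surrogate in the pivotal pharmacokinetic study.

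SAP 8.3.1 gives the method. It first announces a correlation analysis between MCF and the haemostatic efficacy assessment, without naming the bleeds. It then says: "To evaluate the correlation between MCF and the primary efficacy variable Spearman correlation coefficients will be estimated". The coefficients are to be "estimated for the correlation of the 4-point haemostatic efficacy with MCF and with MCF change". Protocol 9.4.2.1 has the same plan.

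SAP 3.2.1 fixes what the primary efficacy variable is: "The primary endpoint is the overall clinical assessment of haemostatic efficacy of Octafibrin in treating the first documented bleeding episode of each patient".

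The data are wider than that. SAP 3.2.2 lists as secondary endpoints "MCF assessment before first infusion and 1 hour after end of first and last infusion of each documented bleeding episode" and "Efficacy of Octafibrin in all bleeding episodes collected in the study", the latter rated on the same 4-point scale. SAP 8.3.4 says that efficacy in all bleeds "will be assessed in the same way as the efficacy of Octafibrin in the treatment of the first bleeding episode per patient". It points to a Section 9.4.1, which is the protocol's number for the primary endpoint analysis and contains no MCF analysis.

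A note in 8.3.1 warns that discriminatory power will be low if outcomes hardly vary. It proposes nothing to offset this.

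**The concern.** The sample is small, the success rate is expected to be high, and each patient contributes one pair. Later bleeds, documented in the same way over a study of up to five years, would add pairs for the same objective, but as worded they do not enter the coefficient.

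At stake is the precision of the evidence linking the surrogate to clinical outcome. An imprecise coefficient could be read as evidence against a good surrogate, or a chance value as support for a poor one. If an all-bleeds correlation is added only after the ratings are known, it will be post hoc. If all bleeds were in fact intended, a plain Spearman coefficient on pooled bleeds would ignore that repeat bleeds come from the same patients. Either reading calls for a clearer sentence in 8.3.1.

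**Working it through.** **Inputs.** N = 24 first bleeds, the minimum (SAP 4.1). True success rate: "assuming a true success rate of 0.95" (SAP 8.2), so failure rate 0.05. The number of bleeds per patient is not given; Protocol 3.3 expects it to differ widely.

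**1. Reproduce the plan's figures.** Exact binomial upper tail, n = 24, p = 0.95, for at least 19, 20, 21 and 22 successes: 0.9990, 0.9940, 0.9702, 0.8841. SAP Table 1 gives 0.999, 0.994, 0.970, 0.884. All four agree.

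**2. Failures among first bleeds.**
- Expected: 24 × 0.05 = 1.2.
- P(0) = 0.95^24 = 0.292.
- P(1) = 24 × 0.05 × 0.95^23 = 0.369.
- P(at most 1) = 0.292 + 0.369 = 0.661.
- At the 90% success rate in protocol version 6.0: 0.90^24 + 24 × 0.10 × 0.90^23 = 0.292. The result therefore depends on the SAP's 95%.

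**3. What this does to a success/failure comparison.** With k failures among n bleeds and no ties in MCF, the largest possible Spearman coefficient is √[3k(n − k)/(n² − 1)]. For k = 1, n = 24 this is √(69/575) = 0.346 (nominal p = 0.097). With k = 0 it is undefined.

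**4. What it does to the planned 4-point coefficient.** With zero or one failure in 24, the ceiling depends on how many ratings are excellent, the rest being good:

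| Excellent ratings | Largest possible coefficient |
|---|---|
| 12 | 0.87–0.88 |
| 16 | 0.82 |
| 20 | 0.65 |
| 22 | 0.48 |

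The one-failure limit therefore does not carry over to the planned coefficient unless almost every rating is excellent.

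**5. Effect of using all bleeds (assumed counts).** Take 24 patients with m bleeds each, 5% failures and intra-subject correlation ρ (beta-binomial). Let p0 and p1 be a patient's probabilities of no failure and of exactly one. Then P(at most 1 in total) = p0^24 + 24 × p0^23 × p1. For m = 2, p0 = 0.9025 + 0.0475ρ and p1 = 0.095(1 − ρ).

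| Bleeds each | Total | ρ | p0 | p1 | P(at most 1 failure) |
|---|---|---|---|---|---|
| 1 | 24 | – | 0.950 | 0.050 | 0.661 |
| 2 | 48 | 0 | 0.9025 | 0.0950 | 0.301 |
| 2 | 48 | 0.1 | 0.9073 | 0.0855 | 0.315 |
| 2 | 48 | 0.3 | 0.9168 | 0.0665 | 0.340 |
| 4 | 96 | 0 | 0.8145 | 0.1715 | 0.044 |
| 4 | 96 | 0.1 | 0.8375 | 0.1305 | 0.067 |
| 4 | 96 | 0.3 | 0.8726 | 0.0781 | 0.119 |

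The independent rows (ρ = 0) are optimistic, since repeat bleeds cluster within patients.

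**The case against.** **The restriction is inferred.** 8.3.1 nowhere says first bleed only; it follows from the term primary efficacy variable. The MCF summaries by outcome and the scatter plots in the same section carry no such limit, so one cannot say that MCF from later bleeds goes unused. This stands, and is why the point is about the wording for the coefficient.

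**The coefficient does not depend on failures alone.** A reader might infer that the objective will rest on at most one failure, or that a null or unstable result is nearly certain. The documents do not support either. The planned scale has four categories, step 4 shows that large coefficients remain possible, and at most one failure is about a two-in-three outcome. Missing ratings and use of other fibrinogen products are set to none (SAP 8.1), which could add failures, although a missing rating carries no information on the surrogate.

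**More bleeds are not a cure.** At a 5% failure rate the ceiling on a success/failure Spearman coefficient stays near √(3 × 0.05 × 0.95) = 0.38 at any sample size; extra bleeds add precision and do not raise that ceiling. Standard formulas for the detectable correlation assume continuous, untied data and would mislead here. Target fibrinogen also differs between minor and major bleeds (Protocol 5.4.2), so post-infusion MCF is likely to vary with severity, and pooling does not remove that. This stands and shapes the fix.

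**One bleed per patient is deliberate and the weakness is disclosed.** Protocol 3.3 gives unequal bleed counts as the reason, but for the primary endpoint. That does not rule out a supportive clustered analysis, and the SAP already plans a repeated-measures model for recovery (8.3.3). Disclosure does not replace using data already in hand.

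**Conclusion.** The point holds as a modest improvement. As worded, the MCF–efficacy coefficient is estimated on about 24 first bleeds, and no correlation over all documented bleeds is planned although both variables are collected for each. At the SAP's 95% success rate, the moderate/none group among first bleeds has at most one member with probability 0.66, which limits the dichotomised summaries. How far the 4-point coefficient is limited cannot be said, because the excellent/good split is not given.

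The gain from all bleeds rests on assumptions outside the documents: with 2 or 4 bleeds per patient and intra-subject correlation 0.1 to 0.3, the chance of at most one failure would be 0.315–0.340 or 0.067–0.119. If few patients bleed more than once, little is gained. No primary conclusion depends on this.

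**What to change.** In SAP 8.3.1, before database closure:

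- State that the planned Spearman coefficients use the first documented bleed of each patient, and keep them.
- Add a supportive association over all documented bleeds: Spearman coefficients of the 4-point rating with MCF 1 hour after the first infusion of each bleed, and with the MCF change to that time. Naming the time also settles a gap, since MCF is taken after both the first and the last infusion and 8.3.1 does not say which enters the correlation.
- Give a confidence interval from a bootstrap that resamples subjects, so that repeat bleeds are not counted as independent.
- Show the result also for minor and major bleeds separately.

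The cost is one extra analysis, with no new data, visits or patients and no change to the primary test. The downside is that frequent bleeders carry more weight; the first-bleed coefficient beside it lets the reader see whether that matters. The subsets by severity may be too small for stable intervals and should be read as descriptive.
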